9.1. Study period and study design

The analysis will be conducted using data from 01 January 2016 through 31 December 2021 or the latest available data at the time of extraction (i.e., the *study period*). Patients will be identified during a *selection window* of 01 January 2017 to 31 October 2021. The date of the first apixaban or LMWH prescription on or within the 30 days following a VTE diagnosis will be termed as the index date. Patients will be required to have continuous enrollment with medical and pharmacy benefits for 12-months prior to the index date to assess study eligibility criteria and to measure baseline characteristics (*the baseline or pre-index period*). Patients will also be required to have continuous enrollment with medical and pharmacy benefits for at least one month (30 days) starting on and following the index date (the follow-up or post-index period) and will be followed through the earliest of the following: health plan disenrollment, index therapy discontinuation, switch to another anticoagulant (includes switch to the other study medication or unfractionated heparin, fondaparinux, warfarin, rivaroxaban, dabigatran, or edoxaban), or end of study period (31 December 2021).

Note: Patients in the LMWH cohort will NOT be considered to have discontinued or switched if they change to an LMWH other than the index LMWH (dalteparin, enoxaparin, or tinzaparin).

Figure 1. Study Period

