9.1.1. Inclusion criteria

Patients must meet all of the following inclusion criteria to be eligible for inclusion in the study:

090177e19b7d94e0\Approved\Approved On: 29-Aug-2023 01:40 (GMT)

Apixaban

B0661183 NON-INTERVENTIONAL STUDY PROTOCOL

Protocol Version: 2.0 29 July 2022

1. Patients with ≥ 1 diagnosis code for VTE (inpatient [primary or secondary discharge diagnosis] or any position on an outpatient non-ancillary medical claim) between January 1, 2017 and October 31, 2021 (selection window).
 - Note: Qualifying outpatient encounters followed by qualifying inpatient encounters within 7 days will be considered an inpatient VTE event, unless LMWH or apixaban was initiated between encounters, in which case it will be classified as an outpatient VTE event
 - First date of claim with a VTE diagnosis code will be termed the ‘index VTE encounter’

2. Evidence of having active cancer, defined as ≥ 2 medical claims with a cancer diagnosis (excluding nonmelanoma skin cancer) on different days during the 6 months before or within 30-days after the index VTE event

OR

≥ 1 medical claim for a cancer diagnosis AND ≥ 1 claim for cancer treatment (eg: chemotherapy, radiation, immunotherapy, hormone therapy or cancer related surgery using national drug codes (NDC), international classification of diseases, tenth revision, clinical modification [ICD-10-CM] procedure codes or healthcare common procedure coding system [HCPCS] codes) during 6 months before or within 30 days after the index VTE encounter

3. ≥ 1 claim of apixaban or LMWH (dalteparin orenoxaparin) on or within 30 days following the index VTE encounter.
 - a. The date of the first apixaban or LMWH prescription fill will be designated as the index date
4. ≥ 12 months of continuous enrollment prior to the index date (pre-index)
5. ≥ 1 months of continuous enrollment including and following the index date (post-index)
 - a. Note: Each patient will have a variable follow-up period with a minimum of 1-month follow-up. Patients will be followed from the day after the index date through the earliest of the following: health plan disenrollment, index therapy discontinuation, switch to another anticoagulant, or study end (December 31, 2021).
 - b. Discontinuation will be defined as occurrence of a ≥ 30 day gap from the run-out of days’ supply of the index LMWH or apixaban prescription. The date of the discontinuation will be defined as the last day of the days’ supply of the last filled prescription.

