9.3.2. All-cause HCRU and Costs Over the Post-Index Period (Post-IPTW)

All-cause HCRU and costs will be reported for the Apixaban and LMWH cohorts over the variable post-index period (minimum 1 month enrollment), post-IPTW. Costs will be reported

PFIZER CONFIDENTIAL

CT24-WI-GL02-RF02 4.0 Non-Interventional Study Protocol Template For Secondary Data Collection Study 01-Jun-2022

Page 23 of 35

090177e19b7d94e0\Approved\Approved On: 29-Aug-2023 01:40 (GMT)

Apixaban

B0661183 NON-INTERVENTIONAL STUDY PROTOCOL

Protocol Version: 2.0 29 July 2022

as per patient per month (PPPM). Over the post-index period, a 30 day period will be used (to represent a month) to ‘standardize’ the period of time for which costs and HCRU will be reported. For each patient, costs will be divided by the variable post-index period in total-person days and then multiplied by 30 to calculate PPPM costs. For example, if a patient has total costs of \$10,000 with 60 days of follow-up, the PPPM will be calculated as $(\$10,000/60) * 30 = \$5,000$.

HCRU will be expressed as both the proportion of patients with such utilization (e.g., the percentage of patients with at least one pharmacy claim, the percentage of patients with at least one physician office visits, etc.) as well as per-patient mean, SD, median and IQR number of visits/services. Costs will be expressed as per-patient mean, SD, median and IQR. Utilization and costs will be calculated on a per patient basis, averaged across the cohort. The denominator will include all patients in the cohort. Costs will be converted to 2021 US dollars (USD) using the medical component of the Consumer Price Index.

HCRU and costs will be reported for mutually exclusive categories: outpatient pharmacy, inpatient hospitalizations, and outpatient care. Outpatient care will comprise the following categories: ER visits, outpatient physician office visits, outpatient surgical visits, laboratory and pathology, radiology and all other services.

All-cause HCRU and costs will be reported for each of the following services:

- Pharmacy
 - Patients with ≥ 1 prescription fill (n, %)
 - Number of prescription fills per patient (mean, SD, median, IQR)
 - Total pharmacy cost per patient (mean, SD, median, IQR)
- Outpatient Services
 - Total outpatient medical care cost per patient (mean, SD, median, IQR)
 - Physician office visits
 - Patients with ≥ 1 physician office visit (n, %)
 - Number of physician office visits per patient (mean, SD, median, IQR)

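### The protocol gives two start days for follow-up and does not say whether the index fill is costed; under the day-after rule, index-drug PPPM cost is understated by about 1/k for a patient with k fills

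*Combined protocol and SAP*

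**What the plan says.** Criterion 3a of section 9.1.1 fixes the anchor: "The date of the first apixaban or LMWH prescription fill will be designated as the index date".

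The start of follow-up is then described in two ways.

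- **Index date included.** Section 9.1 requires enrollment "for at least one month (30 days) starting on and following the index date (the follow-up or post-index period"). The main line of criterion 5 in section 9.1.1 agrees: "months of continuous enrollment including and following the index date (post-index").
- **Index date excluded.** Note 5a, directly under that main line, says: "Patients will be followed from the day after the index date through the earliest of the following".

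Two further rules decide what follows. For patients who discontinue, section 9.1.1 (5b) sets the end of follow-up: "The date of the discontinuation will be defined as the last day of the days’ supply of the last filled prescription". Section 9.3.2 standardizes cost: "costs will be divided by the variable post-index period in total-person days and then multiplied by 30 to calculate PPPM costs".

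Section 9.3.2 includes pharmacy cost in total all-cause cost, which is the first primary objective. Section 9.3.3 leaves pharmacy cost out of the costs tied to recurrent VTE, major bleeding and CRNM bleeding. No section states how a claim dated on the index date is treated in post-index cost.

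**The concern.** The study exists to compare the cost of treating with apixaban and with LMWH, and the index fill is part of that cost for every patient. A programmer who takes note 5a as the costing window drops that fill. The days it supplies remain as follow-up, because discontinuation is dated to the end of supply. Numerator and denominator then no longer describe the same treatment.

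A programmer who takes section 9.1 keeps the fill. Both would be following the protocol, and they would report different values for pharmacy cost and for a primary outcome. Weighting on baseline covariates cannot repair this, because the discrepancy lies in the costing rule.

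The loss is greatest for patients with few fills. Such patients can occur: section 9.2 asks for only 14 days of LMWH use, and no criterion requires a second fill.

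**Working it through.** **The plan's own figure.** Section 9.3.2 gives $10,000 over 60 days. (10,000 / 60) × 30 = $5,000 PPPM, as stated. The formula is sound; the open question is which costs and days enter it.

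**Model.** Take a patient followed to the end of supply, with *k* fills of *d* days each at cost *c* per fill.

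- Index date included: 30·k·c / (k·d) = 30·c / d.
- Note 5a applied to costs: 30·(k − 1)·c / (k·d − 1).
- Share lost: 1 − d(k − 1)/(k·d − 1) = (d − 1)/(k·d − 1), which is roughly 1/k.

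| Fills (k) | 30-day fills: 29/(30k − 1) | 14-day fills: 13/(14k − 1) |
|---|---|---|
| 1 | 29/29 = 100% | 13/13 = 100% |
| 2 | 29/59 = 49.2% | 13/27 = 48.1% |
| 3 | 29/89 = 32.6% | 13/41 = 31.7% |
| 6 | 29/179 = 16.2% | 13/83 = 15.7% |
| 12 | 29/359 = 8.1% | 13/167 = 7.8% |

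Under section 9.1 the share lost is 0% in every row.

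**Effect on the difference between cohorts.** The protocol gives no prices, fill lengths or fill counts by cohort, so these are assumptions: apixaban at $500 per 30 days, LMWH at a multiple of that, 30-day fills. Recorded PPPM is price × 30(k − 1)/(30k − 1). The factor is 150/179 = 0.8380 for six fills and 60/89 = 0.6742 for three.

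| LMWH price | Fills, apixaban / LMWH | True LMWH − apixaban | Recorded LMWH − apixaban |
|---|---|---|---|
| $500 | 6 / 6 | $0 | 419 − 419 = $0 |
| $500 | 6 / 3 | $0 | 337 − 419 = −$82 |
| $2,000 | 6 / 6 | $1,500 | 1,676 − 419 = $1,257 |
| $2,000 | 6 / 3 | $1,500 | 1,348 − 419 = $929 |
| $4,000 | 6 / 6 | $3,500 | 3,352 − 419 = $2,933 |
| $4,000 | 6 / 3 | $3,500 | 2,697 − 419 = $2,278 |

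With equal fill patterns the percentage lost is the same in both cohorts, and the dollar loss differs only through price. These are drug-only figures. Total all-cause cost carries the same dollar shift against a larger base.

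**One-day effect.** The choice of start day also moves every PPPM denominator by one day, a factor of 30/29 = 1.034 at 30 days and 180/179 = 1.006 at 180 days. This is small beside the loss of a fill.

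**The case against.** The strongest reply is that no section excludes the index fill. Section 9.3.2 divides by the post-index period, and the two places that delimit that period, section 9.1 and the main line of criterion 5, both include the index date. Note 5a sits under an enrollment criterion and is not a costing rule. This stands to the extent that the loss is conditional. It does not remove the conflict: section 9.1 gives follow-up and post-index period as names for the same span, and note 5a starts follow-up on a different day.

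A reader might infer that the index fill is costed in neither window. That is not established. It needs the literal reading of note 5a, and the Abstract's variable list allows baseline measures, costs among them, to be taken on the index date as well as before it.

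A reader might also infer that the rule necessarily biases the comparison, or even reverses it. The documents do not support this. Take LMWH at an assumed $600, apixaban at $500, and the approximation that (k − 1)/k of cost is recorded. A true +$100 becomes 300 − 400 = −$100 with two LMWH against five apixaban fills, but 480 − 400 = +$80 with five each. The reversal comes from the assumed fill split.

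Two further limits stand. The 1/k result applies to patients followed to the end of supply; when disenrollment or study end cuts follow-up short mid-supply, the last fill is fully costed while its remaining days drop out, which works in the opposite direction. And Figure 1 and the table shells were not available for this review and may show the intended window.

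**Conclusion.** The contradiction is real and bears on a primary outcome. The protocol's text allows two costing windows: one loses nothing, and the other understates index-drug PPPM by about 1/k for patients followed to the end of supply, and by all of it for a single-fill patient. This goes beyond a missing detail, because following a stated rule as written produces the loss.

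The reach is limited to pharmacy cost and total all-cause cost, with dilution in the total that cannot be sized from the documents. Event-related costs, the other primary objective, lose no fill. Distortion of the comparison between cohorts is plausible, but its size and direction rest on assumed prices and fill counts. The illustration of $1,500 recorded as $1,257 or $929 shows scale only and is not an estimate for this study.

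**What to change.** 1. Amend note 5a in section 9.1.1 so that follow-up begins on the index date, in line with section 9.1 and the main line of criterion 5.
2. State in section 9.3.2 that the index-date claim for the index anticoagulant counts in post-index cost, and that the index date is day 1 of the denominator.
3. State one rule for all other index-date claims. Keep the index VTE hospitalization out of post-index cost, since section 9.3.1 already reports it at baseline.
4. Optionally, report pharmacy and total all-cause PPPM under the day-after rule as a sensitivity analysis, so that readers can see the effect with the study's own prices and fill counts.

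The cost is a few sentences of text and minor reprogramming of the date conditions. No new data are needed.

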9.4. Data sources

This study will utilize data from IQVIA's PharMetrics® Plus. IQVIA's collaboration with Health Intelligence Company, which operates as Blue Health Intelligence, allows IQVIA's bio-pharmaceutical clients sole access to one of the largest United States (US) health plan claims databases and adds IQVIA's market leading health plan claims database. The aggregated database comprises adjudicated claims for more than 190 million unique enrollees across the US. Enrollees with both medical and pharmacy coverage in 2020 represented 40 million lives. Data are available from 2010 onwards, with a typical 4- to 6-month lag due to claims adjudication.

PharMetrics Plus has diverse representation of geography, employers, payers, providers and therapy areas. Patients in each zip code and every Metropolitan Statistical Area of the US are included, with coverage of data from 90% of US hospitals, 80% of all US doctors, and representation from 85% of the Fortune 100 companies. In addition to standard fields such as inpatient and outpatient diagnosis and procedures, retail and mail-order prescription records, PharMetrics Plus has detailed information on the pharmacy and medical benefit (copayment, deductible), the inpatient stay (admission type and source, discharge status) and provider details (specialty, provider identifier [ID]). All zip codes in the US are covered and reported allowing more granular patient segmentation and comparisons by geography. Payment amounts include the negotiated rate between the plan and providers (allowed) and the actual amount paid by health plans to the provider for all services rendered. Charge amount is also available for a subset of claims. Other data elements include dates of service, demographic

PFIZER CONFIDENTIAL

CT24-WI-GL02-RF02 4.0 Non-Interventional Study Protocol Template For Secondary Data Collection Study 01-Jun-2022

Page 27 of 35

090177e19b7d94e0\Approved\Approved On: 29-Aug-2023 01:40 (GMT)

Apixaban

B0661183 NON-INTERVENTIONAL STUDY PROTOCOL

Protocol Version: 2.0 29 July 2022

variables (age, gender, and geographic region), product type (e.g., HMO, PPO), payer type (e.g., commercial, self-insured), and start and stop dates of health-plan enrollment.

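### Death is not named as an end of follow-up, so where enrolment outlasts an in-hospital death, post-death days can enter the PPPM denominator at no cost

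*Combined protocol and SAP*

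**What the plan says.** Section 9.1.1 (5a) follows each patient to "the earliest of the following: health plan disenrollment, index therapy discontinuation, switch to another anticoagulant, or study end (December 31, 2021". Section 9.1 gives the same events: "health plan disenrollment, index therapy discontinuation, switch to another anticoagulant (includes switch to the other study medication" and the other listed anticoagulants, or study end. Neither list contains death. The limitations in section 9.9 do not mention it either.

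Item 5b sets the trigger and the date of discontinuation. The trigger: "Discontinuation will be defined as occurrence of a ≥ 30 day gap from the run-out of days’ supply". The date: "The date of the discontinuation will be defined as the last day of the days’ supply of the last filled prescription".

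Section 9.3.2 forms the cost rate patient by patient: "costs will be divided by the variable post-index period in total-person days and then multiplied by 30 to calculate PPPM costs". The per-patient values are then averaged over the cohort.

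Section 9.3.1 tabulates censoring for two reasons only, switching and discontinuation. Section 9.4 says that the database holds details of "the inpatient stay (admission type and source, discharge status", and also enrolment start and stop dates. The plan does not use discharge status to end follow-up, and it does not say how the enrolment stop date is set when a patient dies.

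**The concern.** All patients have active cancer, and follow-up can run from a 2017 index date to the end of 2021, so deaths on treatment are to be expected. A patient who dies in hospital with drug on hand never refills. Under 5b the discontinuation date is then the run-out date, which lies after death. Unless enrolment stops first, the days in between count as observed time with no cost. If follow-up reaches run-out, the death is also tabulated as a discontinuation.

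All-cause cost is a primary objective (section 8). The records affected are those that end in a terminal admission. Because section 9.3.2 averages per-patient rates, a decedent with short follow-up carries the same weight before IPTW as a patient followed for years. IPTW balances baseline covariates and cannot repair a denominator formed after the index date.

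**Working it through.** **Plan's own figure.** Section 9.3.2: $10,000 over 60 days. 10,000 / 60 × 30 = $5,000, which reproduces.

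**Formula.** Let D be the day of death and e the post-death days that are counted.

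- e = min(unused supply, days from death to recorded disenrolment, days from death to study end). I assume that the 30-day gap in 5b is met, so that run-out is the discontinuation date.
- Recorded PPPM = cost / (D + e) × 30.
- Relative understatement = e / (D + e).

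The documents give no unused supply, day of death or enrolment lag. All values of these below are assumptions.

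**One decedent, $10,000, death on day 60, no earlier disenrolment**

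| Post-death days counted | PPPM | Understatement |
|---|---|---|
| 0 | $5,000 | 0% |
| 7 | 10,000/67 × 30 = $4,478 | 10.4% |
| 15 | 10,000/75 × 30 = $4,000 | 20.0% |
| 29 | 10,000/89 × 30 = $3,371 | 32.6% |
| 89 | 10,000/149 × 30 = $2,013 | 59.7% |

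**Day of death matters.** With e = 29, the understatement is 29/64 = 45.3% for death on day 35, 32.6% on day 60, 29/119 = 24.4% on day 90 and 29/209 = 13.9% on day 180.

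**Enrolment lag matters.** If enrolment stops on the day of death, e = 0 and nothing is lost. If it stops 15 days after death, e is capped at 15. With death on day 60 the loss is then 20.0%, whether 29 or 89 days of supply were left.

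**Cohort mean, illustration only.** Let a fraction f die in hospital on day 60 with a PPPM R times that of the others, with no earlier disenrolment.

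Recorded mean / true mean = [fR × 60/(60+e) + (1−f)] / [fR + (1−f)]

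| | f = 0.05, R = 1 | f = 0.20, R = 5 |
|---|---|---|
| e = 15 | 0.990 / 1.00: −1.0% | 1.600 / 1.80: −11.1% |
| e = 45 | 0.979 / 1.00: −2.1% | 1.371 / 1.80: −23.8% |

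If two cohorts with equal true costs had e = 45 and e = 15, their cost ratio would run from 0.979/0.990 = 0.988 to 1.371/1.600 = 0.857. If enrolment stopped 15 days after death in both, e would be 15 in both and the ratio would be 1.

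**The case against.** The strongest reply is that disenrolment is itself a listed end event and that enrolment stop dates are in the data. If plans close enrolment at death, follow-up ends there and nothing is diluted. That stands: the effect may be zero. What it leaves open is that the plan does not say when enrolment is recorded as ending after a death, so the denominator of a primary endpoint rests on an unstated rule.

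A reader might infer that the understatement is fixed by fill size. It is not. Unused supply is only a ceiling on the days counted; disenrolment or study end may come first, and the percentage also falls as death comes later. Patients may also fill nothing during a long terminal stay, which would shrink the unused supply.

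A reader might also infer a built-in bias between an oral drug and an injectable, since the database holds both retail and mail-order records. The documents do not support this. That sentence describes the database in general and gives no anticoagulant fill lengths. No mortality by cohort is given either. Similar dilution in both cohorts would largely cancel in a cost ratio. The cohort illustration also places every death on day 60. With death on day 180, the widest ratio shrinks from 0.857 to (180/225 + 0.8) / (180/195 + 0.8) = 1.600/1.723 = 0.929.

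Finally, the fix dates only in-hospital deaths. If place of death differed between the cohorts, the dilution that remains could differ too. This is a fair limit and should be stated. The table shells and code lists are separate files that I have not seen, and they may settle some of this.

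**Conclusion.** The point holds in conditional form. Death is not an end-of-follow-up event, and the text available does not prevent post-death days from being counted when enrolment outlasts an in-hospital death. In that case the decedent's PPPM is understated by e/(D+e), which is 20% in the plan's own example with 15 days counted. Only a death whose follow-up reaches run-out is tabulated as a discontinuation; if enrolment ends first, it is not.

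No bias between the cohorts is shown. One arises only if unused supply, mortality or enrolment lag differs between them, and the cohort figures above rest wholly on assumed inputs. The change is worth making because it is cheap, concerns a primary cost endpoint, and does no harm if enrolment already closes at death.

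**What to change.** 1. In sections 9.1 and 9.1.1 (5a), add in-hospital death (discharge status expired, dated at discharge) to the events that end follow-up.
2. In section 9.3.1, give it a censoring row of its own, separate from discontinuation.
3. State how the enrolment stop date is set after a death.
4. In section 9.9, state that out-of-hospital deaths remain undated and may still add time at no cost.

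The cost is one censoring condition from a field already in the database, one table row and two sentences. The drawback is that the correction is partial, since it reaches only deaths in hospital. Reporting in-hospital deaths and the unused supply at death by cohort would show whether the cohorts differ on either.
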